### Intervention:

By study design participants will be randomized twice over the course of their participation. Once at enrollment and again at the time of their second assessment which coincides with the end of their pregnancy. After completing the baseline assessment (T0), participants will be randomized to either the HABIT intervention during pregnancy or to usual care. Usual care consists of the care that pregnant woman usually receive from their obstetric and other providers. All women in the study will continue to receive the care they usually receive. Those in usual care will not receive any extra treatment from the study team. If they are randomized to treatment they will be assigned a coach and will immediately get started with their first session. Treatment during pregnancy will consist of up to 10 in person sessions lasting approximately 20-30 minutes. These sessions will take place at their regularly scheduled OB appointments, at our research building, or a nearby location. Participants in the HABIT pregnancy group will also receive texts and phone calls between sessions. HABIT will focus on weight, physical activity, eating and psychosocial issues. Intervention goals will emphasize adherence to healthy behaviors rather than absolute weight goals. Specifically, women will receive consultation about nutritional balance, dietary guidelines for pregnant women and advice to maintain an optimal rate of weight gain according to prepregnancy BMI. Women will use self-monitoring forms to identify and modify cues for unhealthy behaviors. Beliefs about body weight and eating during pregnancy

will be addressed and effects of physical activity on body weight, health, and mood will be included. Mood will be monitored by the EPDS questionnaire to help tailor individualized treatments. To help facilitate treatment, participants who need them will be provided with smart phones and Bluetooth enabled scales. Participants who are assigned to usual care will not have regular contact with study staff.

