### **Eligibility Criteria**

Women will be eligible if they: (1) have a prenatal BMI  $\geq 25$ ; (2) are at or before 17 weeks and 4 days of gestation; (3) are English speaking and (4) have a singleton pregnancy. We considered an upper limit to BMI. However, given the paucity of data on weight outcomes for women with BMIs >35, we elected not to limit BMI but will randomize women in two strata according to BMI (25-29.9 vs.  $\geq$ 30). Similarly, parity may impact perinatal weight, but intervention goals are similar for primagravidae and multiparous women. Thus, we will recruit women regardless of gravida and parity, and include these variables as covariates in all analyses.

With the approval of modification #20: (5) Identify as Black or Multiracial Black

Infants will be eligible for medical record and microbiome data collection if (1) mothers' are

enrolled into HABIT after MOD16020497-12 or (2) if we are able to reconsent their mothers' during the T1 or T2 timepoints.

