### **Statistical Considerations**

First, we will use descriptive statistics and graphic displays to identify outliers, missing data and patterns of attrition, and to guide decisions about the use of transformations to satisfy the normality assumption. Next, demographic variables and baseline measures will be compared between HABITpreg and TAUpreg and between HABITpost and TAUpost using two-sample t- or Wilcoxon rank sum tests for continuous variables and chi-square or Fisher's exact tests for categorical variables. Data from women who have become pregnant again or for whom pregnancy did not result in a live birth will be excluded.

To utilize the longitudinal data collected, linear mixed-effect models will be the primary analytic tool. Mixed-effect models are useful for longitudinal datasets that contain missing observations, as anticipated in this study, under the assumption of missing at random (MAR). The MAR allows a relationship between missingness (e.g., drop-outs, missed assessments) and outcome through their mutual relationship to other covariates, such as treatment sequences or prepregnancy weight status. No residual relationship between missingness and outcome is required once covariates are taken into account. However, we also will examine patterns of missingness, and report the average effect over different missing patterns if necessary. In each mixed-effect model, we will include group, time, group by time interaction, and the stratification factor, prepregnancy BMI ( $\geq$ 30 or <30) as fixed terms. Subject will be included as a random term to account for repeated measures from the same subject. Different covariance structures will be compared to determine the best model fit.

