There are 8 sequences or combinations of intervention in this SMART, which we use to define group for hypothesis testing. Time also is a generic factor, and the number of levels will depend on the outcome being modeled. For example, for weight, mood and stress, time will be a linear term beginning at baseline, and a quadratic term will be added to the model if necessary. For other outcomes, time will be a factor with 4 levels (baseline, end of pregnancy, and 6- and 12-months postpartum). We also will evaluate the need to control for the effects of potential confounds such as race, age, socioeconomic status (fixed covariates) as well as breastfeeding, smoking status and physical activity (time-varying covariates). If the coefficients for groups or group by time interactions are significant, planned contrasts will evaluate groups on weight and related outcomes at 6- and 12-months postpartum. Additionally, we will create a binary variable for 5% weight loss and use generalized mixed-effect models with the logit link to compare groups on proportions with 5% loss at 6- and 12-months postpartum.

Finally, to fully utilize a SMART design, and to evaluate the utility of using GWG as a tailoring variable, we will explore what the optimal strategy is and for which participants. A dynamic strategy is a decision rule about which intervention is best initially and what intervention follows, depending on the response status. The proposed deisgn produces HABITpreg and TAU during pregnancy, and women who do and do not meet IOM guidelines for GWG each have HABITpost and TAU postpartum, resulting in the 8 possibilities sequences.

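### Time-varying physical activity, breastfeeding and smoking may enter the group models on an undefined test of need, and no model without them is named primary for the randomised contrasts

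*Combined protocol and SAP*

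**What the plan says.** All references are to the combined protocol and SAP.

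- **Method.** Statistical Considerations states that "linear mixed-effect models will be the primary analytic tool".
- **Core terms.** "In each mixed-effect model, we will include group, time, group by time interaction, and the stratification factor", which is prepregnancy BMI at 30 or above versus below 30. A random subject term is added. Eligibility Criteria says of gravida and parity that the team will "include these variables as covariates in all analyses"; Statistical Considerations does not list them.
- **Optional terms.** "We also will evaluate the need to control for the effects of potential confounds". The fixed candidates are race, age and socioeconomic status. The list then continues "as well as breastfeeding, smoking status and physical activity (time-varying covariates".
- **Group.** "There are 8 sequences or combinations of intervention in this SMART, which we use to define group for hypothesis testing". The eight arise because, after either prenatal arm, "women who do and do not meet IOM guidelines for GWG each have HABITpost and TAU postpartum".
- **Contrasts.** Planned contrasts at 6 and 12 months postpartum follow only if a group or group-by-time coefficient is significant.
- **Intervention content.** The Intervention section says, for pregnancy, "HABIT will focus on weight, physical activity, eating and psychosocial issues".

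**The concern.** A confounder of a randomised contrast would have to influence assignment. A variable measured after assignment cannot do that. The plan nevertheless offers post-randomisation variables as candidate confounders, and one of them is a behaviour that HABIT is meant to change. A need test based on association with weight could easily admit activity, because activity is expected to be related to weight.

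Aim 1 asks which combination of interventions gives the best 12-month outcomes. Its natural reading is the total effect of assigning a combination. That is an interpretation, because the documents state no estimand. A model that holds activity fixed answers a different question. With no criterion and no declared primary covariate set, the choice between the two answers could be made after the data are seen. The choice could also decide whether the planned contrasts are reached at all, since they wait on significant group terms.

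**Working it through.** **1. Is there a rule?** No section gives a criterion, a time or a blinding condition for judging need. The primary label attaches to a class of models. The core terms are a minimum, to which the optional ones may be added in the same models. No section calls the adjusted version secondary, a sensitivity analysis or a mediation analysis.

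**2. Timing.** Under Intervention, the first randomisation follows T0 and the second follows T1. Under Study Design & Methods, the activity questionnaire is given at every assessment.

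| Measured at | HABITpreg vs TAUpreg | HABITpost vs TAUpost |
|---|---|---|
| T0 | before assignment | before assignment |
| T1 | after | before |
| T6, T12 | after | after |

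Only T0 precedes both randomisations, so only T0 values are safe for contrasts of the four combinations.

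**3. Is activity a target?** For HABITpreg it is named outright. For HABITpost the evidence is weaker. The behaviour-change measure in Study Design & Methods counts exercise among the topics of HABIT treatment generally. The HABITpost descriptions in Scientific Background and Intervention do not name activity. Neither breastfeeding nor smoking is named as a target of either phase.

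**4. What adjustment does.** The documents give no effect size or standard deviation for this, so there is no plan figure to reproduce and every input below is an assumption. Let A be assignment, M later activity and Y weight, with M = aA + error and Y = dA + bM + error. The total effect is T = d + ab. Write m = ab/T for the share running through activity. With no common cause and no measurement error, the coefficient of A adjusted for M is d = (1 − m)T.

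Take T = −0.40 SD and a = 0.5 SD, so b = mT/a. The check simulated 200,000 subjects per setting at one follow-up time:

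| m | b | d by formula | Simulated, unadjusted | Simulated, adjusted | Share kept |
|---|---|---|---|---|---|
| 0.2 | −0.16 | −0.32 | −0.401 | −0.320 | 0.80 |
| 0.4 | −0.32 | −0.24 | −0.393 | −0.235 | 0.60 |
| 0.6 | −0.48 | −0.16 | −0.396 | −0.157 | 0.40 |

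A repeated-measures version used four randomised combinations, visits T0, T1, T6 and T12, 60,000 women per run and an assumed total T12 effect of −3 kg. For m = 0.1, 0.3 and 0.5 it kept 0.896, 0.695 and 0.511 with time as a factor, and 0.903, 0.707 and 0.504 with linear time. The formula gives 0.9, 0.7 and 0.5.

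**5. What moves these figures.**

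- *Common cause.* Suppose an unmeasured cause acts on activity with coefficient 0.3 and on weight with −0.3, and activity has within-arm variance 1. The adjusted coefficient becomes d + 0.5 × 0.3² = d + 0.045, that is −0.275, −0.195 and −0.115. Simulation gave −0.275, −0.193 and −0.121, keeping 0.69, 0.48 and 0.30. The unadjusted estimate stayed near −0.40. With equal signs the shift is −0.045, so at m = 0.2 the coefficient is −0.365 and the share kept is 0.365/0.40 = 0.91. The bias can go either way.
- *Measurement error.* With classical error and within-arm reliability r, the loss is about m × r. At an assumed r = 0.5, shares of 10% and 50% give losses of 5% and 25%.

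These calculations confirm the mechanism only. They return the share that was put in.

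**The case against.** **Adjustment is optional and a default can be read.** The core terms apply to every model and the rest are only to be considered. A reader might infer that the plan commits to adjusting for activity; it does not. But it also does not make the core model primary, so the choice stays open.

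**Confounder control has a legitimate use.** The sentence serves all the hypotheses. Hypothesis 4 compares women who met their GWG goal with women who exceeded it, which is not randomised. This stands, and that comparison lies outside the point. It does not justify leaving the same option open for the randomised contrasts.

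**The planned group is the eight GWG-split sequences.** This also stands. A reader might infer that leaving activity out would by itself yield the total effect of HABITpreg. It would not, because GWG follows the first randomisation and prenatal comparisons within GWG-defined groups already condition on it. The fix must therefore also define group for these contrasts.

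**The evidence is uneven.** The explicit statement about activity concerns HABITpreg; for HABITpost there is only the general reference to exercise. A reader might also infer that breastfeeding and smoking carry part of the HABIT effect. The documents do not say so. If assignment does not change them, adjusting for them removes no treatment effect.

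**T1 values are valid baselines for the postpartum contrast.** True, but they follow the first randomisation. A single covariate set that serves both contrasts and the four combinations is confined to T0.

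**Missing data may call for covariates.** The plan's own examples of covariates that explain missingness are treatment sequence and prepregnancy weight status, not later activity.

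**Conclusion.** The point holds in a limited form. The plan lists a post-randomisation treatment target as a candidate confounder, gives no rule for admitting it, and names no primary covariate set. If activity is admitted, the HABIT contrast is no longer the total effect of assignment and may carry bias from unmeasured common causes.

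The harm is conditional and its size is unknown. A reader might take the shrinkage of 10% to 50%, or any other figure above, as a forecast for this trial. It is not: no section gives the share of effect running through activity, the reliability of its measurement or the strength of common causes. The conclusion rests on reading Aim 1 as a question about total effects, and it covers HABITpreg vs TAUpreg, HABITpost vs TAUpost and their four combinations. The case is firmest for activity and HABITpreg, weaker for activity and HABITpost, and one of timing only for breastfeeding and smoking. The plan should be changed on this point, but the defect does not undermine the design.

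**What to change.** Add to Statistical Considerations, in substance:

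> For the randomised contrasts (HABITpreg vs TAUpreg, HABITpost vs TAUpost and their four combinations), group is defined by the two assignments and not by GWG status. The primary model contains group, time, group by time, BMI stratum, gravida, parity and any prespecified covariates measured at T0, because T0 precedes both randomisations. Models that add post-randomisation physical activity, breastfeeding or smoking are secondary or mediation analyses and will be labelled as such.

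Name the T0 covariates in advance. This also brings gravida and parity, now only in Eligibility Criteria, into the stated model. Adjustment in comparisons that depend on GWG status, such as Hypothesis 4, should be handled separately.

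The cost is a few sentences. No data are added, no planned analysis is lost and participants bear no burden.

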**Protocol Date: 11/20/2024** 

### **Scientific Background**

Approximately two-thirds of American women are overweight or obese (OV/OB; BMIs > 25), and rates of obesity prior to pregnancy are increasing dramatically. For example, Kim and colleagues reported a 70% increase in the prevalence of pre-pregnancy obesity over a 10 year period. Rates of gestational diabetes mellitus (GDM), pre-pregnancy hypertension, and preeclampsia also have increased since 2000, and women who are OV/OB prior to pregnancy are at higher risk for preeclampsia, and gestational hypertension than are normal weight women. Prenatal OV/OB, along with weight gain in pregnancy, is related to difficult deliveries, an increased likelihood of macrosomia, congenital malformations, and obesity among the children born to OV/OB mothers.

Gestational weight gain (GWG) also affects maternal and child health independent of prepregnancy OV/OB. Excessive GWG robustly predicts the amount of postpartum weight retention, increases the risk of obstetric complications and is associated with adiposity among neonates, children, adolescents, and adults. The Institute of Medicine (IOM)reissued guidelines for GWG stratified by pre-pregnancy BMI that recommend GWG between 15 and 25 pounds for an overweight woman and 11 to 20 pounds for an obese woman. However, approximately 45% of women exceed IOM guidelines for GWG, and rates above 50% and as high as 63% have been reported. Moreover, women who begin pregnancy OV/OB are more likely to exceed IOM guidelines for GWG than are women with pregravid BMIs in the healthy weight range, and some evidence suggests that overweight women are even likelier than obese women to exceed GWG guidelines. Thus, although the causes of obesity are multi-factorial, the perinatal period is uniquely associated with women's obesity and offers a critical window for improving maternal health.

Perinatal interventions have not succeeded in decreasing GWG or affecting weight at one year postpartum.

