## **Study Objectives**

The purpose of this study is to determine the best combination of lifestyle intervention to improve maternal weight, health and psychological symptoms at 1 year postpartum.

Specific Aim 1: Determine the combination of prenatal and postpartum lifestyle interventions that optimizes maternal weight, cardiometabolic health, depressive symptoms and stress at 12-months postpartum.

Hypothesis 1: Women in HABITpreg who are assigned to HABITpost will have improved weight and secondary outcomes at 12-months postpartum relative to women who receive only HABITpreg or only HABITpost.

Hypothesis 2: Women who receive only HABITpost will have improved weight and secondary outcomes at 12-months postpartum compared to those who receive only HABITpreg or only TAUpost.

Specific Aim 2: Determine the optimal combination of interventions based on GWG that improves weight, cardiometabolic health, depressive symptoms and stress at 12-months postpartum.

Hypothesis 3: Among women who receive HABITpreg or TAUpreg and gain excessive GWG, those who are assigned to HABITpost will have improved weight and secondary outcomes at 12-months postpartum compared to those in TAUpost.

Hypothesis 4: Among women who receive HABITpost, women who met GWG goals will have improved weight and secondary outcomes compared to those who exceed GWG goals regardless of prenatal assignment.

Exploratory Aims: Evaluate the optimal sequence of interventions by prenatal weight. We will determine, for example, if the strategy of HABITpreg then HABITpost, regardless of GWG, optimizes outcomes for obese women, and if TAUpreg then HABITpost is helpful for overweight women only when GWG is excessive. Evaluate the effect of the sequence of interventions on infant risk for obesity.

Impact: This SMART is designed to identify the sequence of interventions most likely to improve maternal health at one year postpartum. Optimizing the sequence of behavioral interventions to address specific needs during pregnancy and the first postpartum year can maximize intervention potency and mitigate longer-term cardiometabolic health risks for women and their children.

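### The omnibus test that unlocks the planned contrasts is run on groups defined partly by gestational weight gain, so it can pass when no intervention works and cannot be relied on to protect H1 and H2

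*Combined protocol and SAP*

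**What the plan says.** Statistical Considerations defines the unit of testing: "There are 8 sequences or combinations of intervention in this SMART, which we use to define group for hypothesis testing". Later in that section it explains how the eight arise: there are two prenatal conditions, and "women who do and do not meet IOM guidelines for GWG each have HABITpost and TAU postpartum, resulting in the 8 possibilities sequences". Group is thus prenatal arm × GWG status × postpartum arm, and four of the eight groups are excessive gainers by definition.

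Contrasts depend on a significant group or group-by-time result: "If the coefficients for groups or group by time interactions are significant, planned contrasts will evaluate groups on weight and related outcomes". They are made at both 6 and 12 months after delivery. The available text gives no alpha, testing order or multiplicity adjustment.

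Study Objectives states H1 and H2 for 12 months, each with two comparators. H1 sets women given both interventions "relative to women who receive only HABITpreg or only HABITpost". H2 sets women given only the postpartum intervention "compared to those who receive only HABITpreg or only TAUpost".

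Scientific Background states: "Excessive GWG robustly predicts the amount of postpartum weight retention".

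**The concern.** An omnibus test protects later treatment contrasts only if its null hypothesis is that treatment does nothing. The null here also says that GWG status makes no difference to weight, which the protocol's background contradicts. A significant result therefore need not be evidence that either intervention works.

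This condition is the only stated safeguard on the planned contrasts. If GWG alone can satisfy it, a trial of two ineffective interventions may go on to several H1/H2 contrasts with nothing stated to limit the chance of a false positive. The protection also varies with the strength of the GWG effect, the sample size and the form chosen for time, none of which reflects treatment.

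**Working it through.** The plan gives no alpha, sample size, power or family-wise error, so there is no figure to reproduce. Assumed throughout: two-sided 0.05 per test, four equal treatment arms, and each arm's mean taken over its two GWG groups.

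**1. How often the omnibus test passes when no intervention works**

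At a single time point the eight-group F test has 7 and N − 8 degrees of freedom. If a share p are excessive gainers and they differ by d standard deviations, the noncentrality is λ = N·p(1 − p)·d². With p = 0.5, λ = N·d²/4. Scientific Background supports a share near this: "approximately 45% of women exceed IOM guidelines for GWG, and rates above 50% and as high as 63% have been reported". Across 45-63%, p(1 − p) runs from 0.2475 to 0.2331, so λ changes by at most 7%.

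| Assumed N | d = 0 | d = 0.5: λ | d = 0.5: chance of passing |
|---|---|---|---|
| 160 | 5% | 10 | 59% |
| 240 | 5% | 15 | 81% |
| 320 | 5% | 20 | 92% |
| 400 | 5% | 25 | 97% |

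For weight the plan uses linear time, with a quadratic term if needed. Longitudinal simulations with no intervention effect (assumed 200-400 women and illustrative GWG effects) gave:
- Linear time: passes in 23-80% of trials, with a 12-month false-positive chance of 7-14%.
- Group-specific quadratic or four-level time: passes in 89-100%, with 14-17%.
- Linear time plus a quadratic common to all groups (240 women, group-by-time test only): passes in 1%, 23% and 98% when 0.3, 0.5 and 0.7 kg of 12-month weight is carried per kg of GWG.

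**2. False positives once the condition is met**

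Write the arms as HH, HT, TH, TT (prenatal then postpartum; H = HABIT, T = usual care). Read pairwise, and taking H2's second comparator as TT, H1 is HH−HT and HH−TH; H2 is TH−HT and TH−TT. Each statistic is z = (difference in means)/√(2σ²/n). Contrasts sharing an arm correlate at ±0.5; HH−HT and TH−TT are uncorrelated.

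- If independent: 1 − 0.95⁴ = 18.5%.
- With the actual correlations, by simulation: **15.6%** at 12 months.
- Counting only errors in the hypothesised direction: 8.6%.
- Comparators pooled within each hypothesis (two contrasts): 9.7%.

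Adding 6 months, for an assumed correlation between the two times:

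| Correlation | 0.5 | 0.8 | 0.9 | 0.95 | 0.99 |
|---|---|---|---|---|---|
| At least one false positive | 27% | 23% | 21% | 20% | 17% |

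**3. Alternatives at 12 months**

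- Omnibus test on the four randomised arms (3 df), then the four contrasts unadjusted: about 4.5% when nothing works.
- The same rule when TT alone differs strongly: the omnibus test passes almost always, and the three true null contrasts carry about 12%.
- Requiring both comparators to be beaten, with no omnibus test: 0.9% when nothing works and about 3% when only TT differs. In general, a false claim of H1 needs at least one comparison with no true benefit to be significant in the favourable direction, which has a chance of at most 2.5%. The same holds for H2, so the total is at most 2.5% + 2.5% = 5%.
- Power: if each contrast has 80%, both are significant in about 69% of trials, and at least one in 0.80 + 0.80 − 0.69 = 91%. Adding Holm lowers the power to claim H1 from 69% to about 51%.

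**The case against.** The plan never calls the omnibus test a multiplicity control and never says the contrasts are unadjusted; it is silent. That is fair, and the point does not need more. The condition is the only safeguard written down, and its null hypothesis is the wrong one for H1 and H2.

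A reader might infer a fixed family-wise error of 16-21%. The documents do not support that. The figures apply after the condition is met and rest on an unstated alpha, equal cells and a pairwise reading. The upper figure also needs a correlation near 0.9 and counts 6-month contrasts, which H1 and H2 do not name. Both hypotheses are directional, which roughly halves the count of errors that would support them.

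A reader might also infer that the omnibus test always passes. That result comes from time as a four-level factor, which the plan reserves for outcomes other than weight, mood and stress. In the setting where the group-by-time test passes 1% of the time, false positives through that route cannot exceed 1%.

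Finally, the eight groups have a use: H3 and H4 are defined by GWG status. This stands, and is a reason to change the omnibus test for H1 and H2 only.

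**Conclusion.** The concern holds in conditional form. The stated condition can be met by GWG differences alone, because its groups contain a non-randomised post-baseline variable that the protocol treats as prognostic. How often this happens cannot be fixed from the documents: about 5% of trials with no GWG effect, and about 60-97% with a 0.5 SD effect at one time point. The GWG effect and sample size are not given, and the time form is left partly to the data.

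When the condition is met, the chance of a false significant H1/H2 contrast is about 16% at 12 months under the stated assumptions, and between about 9% and 27% across the readings shown. Secondary outcomes, H3, H4 and the separate comparison of 5% weight loss are not counted. This should be corrected before analysis, but it does not invalidate the randomised comparisons themselves.

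**What to change.** For H1 and H2, run the omnibus test on randomised factors only: prenatal arm, postpartum arm and their interaction, for 12-month weight (3 df). State the alpha and sidedness.

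Because that test does not protect once one arm truly differs, also state that H1 and H2 are each claimed only if both named comparators are beaten. Holm is then unnecessary; it is an alternative only if each contrast is to be claimed separately.

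Label 6-month and secondary-outcome contrasts as supportive. Keep the GWG-defined groups for H3, H4 and the exploratory strategy analysis.

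The change is to SAP wording, with no new data. The downside is power: at an assumed 80% per contrast, requiring both comparators gives about 69% per hypothesis, against about 91% if either one sufficed.

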Height, weight & waist circumference. Height will be measured with a stadiometer at study enrollment (T0). Weight will be measured using a calibrated digital scale at all assessment timepoints. Women will be measured in street clothes without shoes. Prepregnancy body mass index (BMI) will be calculated as (weight in kg)/(height in m2). The use of self-reported pregravid weight is common in studies of gestational weight gain and accurate within 1-2 kg. Repeated measurements of weight will also be abstracted from medical charts during pregnancy. Waist circumference will be measured at T0, T6 and T12. This will be taken using a tape measure marked in centimeters and placed at the level of the umbilicus. The average of two consecutive measurements will be used.

Gestational weight gain and excessive gestational weight gain. Gestational weight gain (GWG) will be calculated as final weight before delivery minus prepregnancy weight. GWG will be defined as excessive according to IOM guidelines based on initial prepregnancy BMI. Both the categorical (yes/no) variable representing GWG above the IOM guideline for the woman's prepregnancy BMI, and the total amount of GWG will be used as dependent variables. Because the length of gestation is a potential confounder of GWG, we will abstract delivery date from women's medical charts and calculate gestational length.

Demographic information. Information including age, race, ethnicity, income, educational background, employment status, health insurance status and marital status will be collected at T0 and updated at T1, T6 and T12.

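### The 6- and 12-month weight contrasts, most naturally read as differences in level, are not adjusted for T0 weight, which costs precision if weight is highly correlated between visits

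*Combined protocol and SAP*

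**What the plan says.** Under Statistical Considerations the model is specified so: "In each mixed-effect model, we will include group, time, group by time interaction, and the stratification factor, prepregnancy BMI", in two levels (30 or above, or below), with subject as a random term. T0 weight enters as a response, because "for weight, mood and stress, time will be a linear term beginning at baseline"; a quadratic term is optional. Contrasts are conditional: "If the coefficients for groups or group by time interactions are significant", then "planned contrasts will evaluate groups on weight and related outcomes at 6- and 12-months postpartum".

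Neither the fixed terms nor the possible confounders listed in that section include T0 weight. Gravida and parity are added as covariates under Eligibility Criteria. No common baseline mean is stated. A separate binary endpoint is planned ("we will create a binary variable for 5% weight loss").

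On timing, the Intervention section says "After completing the baseline assessment (T0), participants will be randomized", and that all women are randomised again after T1. Under Study Design & Methods, "Weight will be measured using a calibrated digital scale at all assessment timepoints". Baseline weight therefore precedes both randomisations and is already collected.

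**The concern.** A T0 value in the response vector does not by itself adjust a visit-level contrast. With a free group effect, the difference between groups at 12 months is the group coefficient plus the group-by-time part, and it carries the between-woman spread in body size. The BMI stratum removes some of that spread, but it has two levels and the trial sets no upper BMI limit.

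What is at stake is precision and exposure to chance imbalance at T0. With time as a factor, a chance T0 difference d passes into a level contrast as r × d and into a change contrast as −(1 − r) × d; at r = 0.9 these are 0.9d and −0.1d. Because the text does not exclude a change contrast, the choice between two contrasts of possibly very different precision could also be made after the data are seen.

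**Working it through.** **Plan's own figure.** There is none to reproduce: the documents state no sample size, SD, correlation or target difference.

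**Inputs from the documents.** Four visits (T0, T1, T6, T12); group, linear time, group by time and BMI stratum as fixed terms; a random subject term; T0 as a response.

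**Assumptions.** Equal variance within stratum, set to 1; correlation r between any two visits (compound symmetry, as a random subject term implies); complete data; visits at t = 0, 5, 12 and 18 months from T0. The per-group sample size cancels in the ratios.

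**Sums.** Σt = 35, mean 8.75, Σt² = 493, Sxx = 493 − 35²/4 = 186.75.

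**Variances at 12 months postpartum (t = 18), linear time**
- Level: r + (1 − r)[1/4 + (18 − 8.75)²/186.75] = r + 0.708(1 − r)
- Change from T0: (1 − r) × 18²/186.75 = 1.735(1 − r)
- Common baseline mean, T0 kept as a response: 324(1 − r)/[493 − 1225r/(1 + 3r)]
- T0 as covariate, three later visits as responses: (1 − r)(r + 0.807)

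| r | Level | Change | Common baseline | SE level / common baseline | SE reduction, common baseline vs change |
|---|---|---|---|---|---|
| 0.5 | 0.854 | 0.867 | 0.653 | 1.14 | 13% |
| 0.8 | 0.942 | 0.347 | 0.316 | 1.72 | 4.5% |
| 0.9 | 0.971 | 0.173 | 0.166 | 2.42 | 2.1% |
| 0.95 | 0.985 | 0.087 | 0.085 | 3.41 | 1.0% |

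Example at r = 0.9: 1225 × 0.9/3.7 = 298.0; 493 − 298.0 = 195.0; 32.4/195.0 = 0.166; √(0.971/0.166) = 2.42.

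**Level against change directly.** The SE ratio is 0.99, 1.65, 2.37 and 3.37 at the same four values of r. The two readings are equivalent near r = 0.5 and far apart at 0.9.

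**Form of time.** With time as a factor, level/T0-covariate SE is 1/√(1 − r²) = 1.15, 1.67, 2.29 and 3.20, so the result does not depend on linearity. Moving the visits to 0, 4.5, 11.5, 17.5 or to 0, 6, 12.5, 18.5 changes the 12-month level/change ratio at r = 0.9 only to 2.38 and 2.33.

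**Which adjustment, at 6 months (t = 12), linear time, r = 0.9**
- Change: 0.771 × 0.1 = 0.0771
- T0 covariate: 0.1 × (0.9 + 0.335) = 0.1235
- Common baseline: 144 × 0.1/195.0 = 0.0738

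The covariate SE is √(0.1235/0.0771) = 1.27 times the change SE and √(0.1235/0.0738) = 1.29 times the common-baseline SE. At 12 months the covariate form falls behind change only when r + 0.807 exceeds 1.735, that is, above r of about 0.93; at r = 0.95 its SE is 0.6% larger.

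**The case against.** **The contrast is clear enough.** The aims and the analysis text speak of weight at a visit, which points to levels. This largely stands. A reader might infer that the plan leaves three readings equally open: level, change and baseline-adjusted. It does not. Nothing in the text supports the adjusted reading, and the trigger on group or group-by-time coefficients decides when contrasts are run, not their scale. A reader might also infer that Hypothesis 3 lacks a reference for improvement, but it names its comparator: "those who are assigned to HABITpost will have improved weight and secondary outcomes at 12-months postpartum compared to those in TAUpost". What remains is that the level reading is the imprecise one when r is high, and that change is not ruled out. The 5% loss endpoint is separate and does not settle the continuous contrast.

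**The BMI stratum already adjusts.** Only in part. The r above is within stratum, so this is allowed for. If the stratum explained 40% of weight variance (an assumption), an overall correlation of 0.9 would become (0.9 − 0.4)/0.6 = 0.83 within stratum, and the two-visit level/change SE ratio would still be 1/√(2 × (1 − 0.833)) = 1.73.

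**The size is hypothetical.** This stands. No correlation is documented, the plan will compare covariance structures, and the level and change readings have about the same SE at r = 0.5.

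**One remedy does not suit every comparison.** This also stands. The 8 groups are partly defined by GWG, but that is no reason to bar a common baseline for HABITpost against TAUpost within one prenatal arm and GWG category: all women are re-randomised after T1 and HABITpost starts after delivery. Using the covariate form there would cost about 29% in SE at 6 months with linear time and r = 0.9.

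**Conclusion.** The concern holds as a matter of precision. On its most natural reading, the contrast omits an adjustment that is available from data already collected. At 12 months the level SE is 1.14 to 3.41 times the common-baseline SE for r from 0.5 to 0.95. If change from T0 was intended, the 12-month gain is between 13% and 1.0%, and naming the scale is most of what is needed. Less correlated outcomes, such as mood or stress may be, would sit towards the lower end of r: the penalty for levels is smaller there, and the gain over change larger.

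These sizes rest on an assumed r, compound symmetry and assumed visit times. A reader might infer that the randomised comparisons are biased; the documents do not support that, since T0 is measured before both randomisations. Comparisons across GWG categories (Hypothesis 4) differ: GWG is not randomised, so groups may differ at T0, and level and change contrasts need not agree even in expectation.

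**What to change.** State in Statistical Considerations that the 6- and 12-month contrasts for continuous outcomes are T0-adjusted, and with which form of time.

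- **Randomised comparisons:** keep T0 as a response and give the compared groups a common baseline mean. This covers the first-stage arms, and HABITpost against TAUpost within the same prenatal arm and GWG category (Hypothesis 3). T1 also precedes the second randomisation, so say how it is handled there.
- **Comparisons across GWG categories (Hypothesis 4):** do not impose a common baseline. Use T0 as a covariate with post-baseline visits as responses, or a stated change from T0, and note that neither makes the comparison randomised.
- **Throughout:** never use T0 as both covariate and response in one model.

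The cost is slightly more analysis wording and no new data. The drawback is confined to the covariate form under linear time: its SE is 27% larger than that of a change contrast at 6 months when r = 0.9, and marginally larger at 12 months when r is above about 0.93.
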